### **Intervention Toolbox**

Participants are provided with a toolbox of options to help with their personalized behavior goals. Participants can choose different tools at each in-person session and can keep tools for the duration of the study or trade them in for new tools as desired. All participants are encouraged to use a wrist-worn device (eg, Watchminder) that provides reminders to engage in the behavior. The wrist-worn device is programmed to vibrate and display the message *Rise Up* periodically from 8 AM to 9 PM every day; however, participants have the option to change these times to match their personalized action plan. For participants in the Reduce Sitting arm, the reminder is set to once an hour. For participants in the Increase Transitions arm, the reminder is set to every 20 minutes. Other tools offered to help prompt behavior change include lists of computers, tablets, and phone apps that prompt sitting breaks; egg timers; and visual reminders (cue cards and a study-branded bracelet). Participants in the Reduce Sitting arm have the option of a standing desk to use at home or work starting in week 2, and participants in the Increase Transitions arm have the option of a tally counter to count transitions throughout the day.

### **Healthy Living**

Participants in the healthy living attention control (Healthy Living) condition receive an equal number of contacts as those in the 2 intervention arms. The first session (week 1) is delivered in-person, whereas the remaining

sessions (weeks 2, 3, 4, 6, 8, and 11) are delivered over the phone. During the first session, the health coach provides an overview of the study group and gives the participant a folder that includes information, worksheets, and resources on various healthy aging topics that may be discussed throughout the study. A new healthy aging topic is discussed at each session, with sleep and aging as the first topic. For all future phone sessions (weeks 2, 3, 4, 6, 8, and 11), the participant chooses which healthy aging topic to discuss. Example topics include safe driving, stress reduction, and healthy bones (Figure S1 in Multimedia Appendix 1). At each session, the health coach first provides an introduction to the selected topic. The health coach then reviews the learning objectives for the session, provides additional information about the health topic, and prompts the participant to complete the topic's worksheet. Then, the health coach and participant set the goal of the participant's choice related to the topic for that session and develop a related action plan. Using motivational interviewing techniques, confidence is assessed and supported using a 0-10 ruler question. At the end of each session, the health coach summarizes the session and confirms the date and time of the next session. The initial in-person session lasts 60 minutes, and subsequent phone sessions last 30 minutes.

## COVID-19 Considerations

Owing to the COVID-19 pandemic, temporary pauses in enrollment of new study participants and in-person sessions occurred and may continue to occur consistent with UC San Diego research policies and San Diego County health orders. To minimize data loss during the pause of in-person visits, enrolled participants whose final 3-month assessment visits are scheduled during office closures will be asked to complete measures remotely. For remote measures, the participants are mailed an automated blood pressure machine and a measuring tape. A Zoom videoconferencing session is scheduled to obtain the blood pressure, waist and hip circumferences, balance tests, chair raises (as part of the SPPB), and NIH Toolbox measures (oral symbol digit test and the list sorting working memory test) using the NIH Toolbox recommendations for remote delivery]. Participants are mailed activPAL and ActiGraph to objectively measure sedentary time and sit-to-stand transitions per protocol on the due date. Survey measures through REDCap (Research Electronic Data Capture) are emailed to participants on the due date. Participants are offered extended phone coaching with continued behavior change support until they are able to complete a blood draw either via mobile phlebotomy that goes to their home or upon our ability to conduct in-person assessments. Additional measures of anxiety (PROMIS Bank v.10–Anxiety and Cognitive and Affective Mindfulness Scale–Revised [CAMS-R]) have been added to better understand how anxiety and stress during this period relate to behavior change.

The study protocols may continue to shift to support remote delivery and to respond to the changing requirements related to the COVID-19 pandemic to maintain safety for participants and study staff.

## Measures and Outcomes

### Primary Outcomes

#### Glucose Regulation and Blood Pressure

The primary outcomes are glucose regulation and blood pressure assessed at baseline and at 3 months. Glucose regulation will be assessed by fasting plasma insulin and glucose, HbA1c, and HOMA-IR. Fasting blood (45 mL) is collected in EDTA and Li-Heparin vacutainers. Frozen processed samples will be stored in locked freezers at -80 °C. Plasma and whole blood samples will be used for glucose and HbA1c assays, and all analyses will include normalization and quality control standards. HbA1c is measured in whole blood in real time (DCA Vantage, Siemens). After blood sample collection is complete, fasting plasma glucose will be measured using the standard glucose oxidase method (YSI Bioanalyzer) and fasting plasma insulin will be measured using an immunoassay kit (Meso Scale Discovery, catalog #K151BZC). Standard curve samples and quality control replicates (minimum of 2 per plate) will be run on each assay plate. Linear dilution and spike-in controls will also be included in each assay run. Additional aliquots of samples will be stored at -80 °C should repeat analyses be required and also for future ancillary analyses. Blood pressure is measured using the Dinamap or Accutor 7 or Dinamap V100 blood pressure monitor after participants have rested while seated for at least 5 minutes. Measures are taken at least three times, and the mean of the second and third readings will be calculated.

#### Objective Measure of Sitting Time and STS Transitions

Measures used to examine the dose-response effects of behavioral changes on glucoregulatory biomarkers and blood pressure are activPAL and ActiGraph GT3X+. For 7 days before the baseline and 7 days before the 3-month final visit, participants are asked to wear the 2 devices for 24 hours a day. activPAL is a small and

lightweight accelerometer worn on the anterior aspect of the thigh that produces a signal related to thigh inclination, which is used to estimate the time spent in different body postures (sitting and standing) and the number of sit-to-stand transitions. activPAL has demonstrated good reliability and validity. activPAL data will be downloaded using activPAL Professional Research Edition software package using the 15-second Epoch. To filter nighttime sleeping, participants are asked to keep a sleep log each night they wear the activPAL. ActiGraph GT3X+ is a small device attached to a belt, positioned over the right hip. The ActiGraph collects data on 3 axes at 30 Hz to estimate the minutes spent in sedentary, light, moderate, and vigorous activity using calibration thresholds. ActiGraph has been validated against heart rate telemetry and total energy expenditure. Nonwear time will be classified using Choi algorithm with 90 consecutive zero counts on the x-axis. We will use the newly validated OPACH cut points to assess moderate PA. In addition, data will be provided to the Biostatistics Core and project 3 for further analysis of bouts, time of day, and clustering with sleep and to validate the machine-learned algorithms.

### **Secondary Outcomes**

Secondary outcomes focus on physical, emotional, and cognitive function and will be measured at baseline and at 3 months. Objective lower extremity functioning will be measured using the SPPB to measure balance, gait speed (4 meters course), and chair stand. Self-report physical functioning will be measured using 6 items from the Activities of Daily Living Survey, which focuses on the ability to perform basic tasks of everyday life, such as eating, bathing, or dressing with or without assistance. Physical and emotional functioning will be measured using the Physical Functioning Survey (SF-36). It comprises 36 items that assess 8 health concepts: physical functioning, role limitations caused by physical health problems, role limitations caused by emotional problems, social functioning, emotional well-being, energy or fatigue, pain, and general health perceptions. SF-36 has been found to be reliable, valid, and responsive for a variety of medical diagnoses. Depressive symptoms will be measured using the validated 10-item Center for Epidemiologic Studies Depression Scale short form. These outcome measures were selected for consistency with the outcome measures used in the cohort for project 3 of the STAR program.

Objective cognitive functioning will be measured using the Dimensional Change Card Sort, List Sorting Working Memory, and Oral Symbol Digit from the NIH Toolkit. These tests assess executive function, memory, and processing speed, respectively. These 3 tests take about 17 minutes to administer via an iPad (Apple Inc) app and have been validated and normed in individuals aged 3-85 years. Self-report cognitive functioning is assessed using the 8-item Cognitive Function Questionnaire from the Patient-Reported Outcomes Measurement Information System (PROMIS).

### **Additional Measures**

As psychosocial factors may mediate and moderate sedentary behavior changes, these domains are also measured. Self-reported perceptions of sleep quality, sleep depth, and restoration associated with sleep are measured using the NIH PROMIS Sleep Disturbance 8a Short Form. Self-reported barriers and benefits related to sitting are assessed on a 9-item, 5-point Likert scale assessing the mental and physical factors that affect their ability to sit adapted from a scale for PA. Participants are asked to rate their confidence in performing the targeted sedentary behaviors (sitting reduction and increase in sit-to-stand transitions) on a 2-item confidence scale, which is modeled after a PA self-efficacy scale. Self-reported PA is measured at baseline using the Community Healthy Activities Model Program for Seniors (CHAMPS) Physical Activity Questionnaire for Older Adults, which asks about weekly frequency and duration of a variety of lifestyle physical activities that are meaningful and appropriate for older adults. CHAMPS was selected for measurement consistency across all the STAR projects. Anxiety will be assessed using the NIH PROMIS computer-adaptive version of their anxiety measure. CAMS-R is a 12-item measure that captures mindful approaches to thoughts and feelings. Pain will be measured using the PROMIS pain interference NIH PROMIS pain interference and intensity short forms and modified items recommended by the NIH Task Force for Research Standards for Chronic Low Back Pain. Additional measures that were adapted from validated measures to specifically address sedentary behavior include the Self-Report Behavioral Automaticity Index and habits and perceptions.

Sedentary Behavior Interrupted:
A Randomized Trial of 3-Month Effects on
Biomarkers of Healthy Aging and Physical
Functioning in the Real World (P2)

NCT03473145

August 26, 2025

Statistical Plan

Baseline characteristics were compared across the 3 treatment arms using ANOVA for continuous variables and χ^2 or Fisher exact tests for categorical variables. Study-related adverse events were tabulated by group using a standard medical dictionary for regulatory activities body system categories.

The primary analysis comparing the sit less and sit-to-stand interventions with the healthy living controls used the intent-to-treat principle. Linear mixed models (LMMs) were applied, allowing for the inclusion of partially complete records, thereby reducing complete case analysis biases. The model included baseline and 3-month outcomes as dependent variable; time (baseline, 3-month), group (active, control), and the group*time interaction were fixed-effect independent (categorical) variables. A subject-specific (random) intercept was included to model individual heterogeneity in outcomes. A significant group*time interaction indicated that outcome changes differed between that intervention and the control arm; this difference of outcome changes between intervention and control arms represents the intervention effect.

To reduce the chance of false positives, we first fit the aforementioned LMMs for 2 primary composite outcomes: (1) glucoregulatory outcomes defined as the average of 4 Z scores of insulin, glucose, HbA1c, and HOMA2-IR; and (2) blood pressure composite defined as the average of 2 Z scores of systolic and diastolic blood pressure. The Z score for each participant for a specific marker and time point was derived by subtracting the sample baseline mean from the participant's marker value at that time point and dividing this difference by the sample baseline SD. This composite score analysis represents an omnibus test of intervention efficacy across multiple (correlated) outcomes: rejection of the null hypothesis would suggest that the intervention (compared with controls) effected changes across components of the composite score. After this composite score analysis, we compared group differences for each of the outcomes; we present intervention results for the individual markers.

Several secondary analyses were conducted. First, we evaluated intervention effects adjusted for baseline stratification variables (obesity status, employment status). Second, we evaluated group differences in outcomes between the 2 intervention arms. Third, we evaluated changes in physical activity (standing, stepping, light physical activity, and MVPA) by intervention arm. Fourth, we included an indicator variable for COVID-19 (yes or no) and evaluated 3-way COVID-19*group*time interaction (by likelihood ratio tests) to test whether changes in outcomes differed between participants with delayed 3-month assessment because of COVID-19 and those who received the original protocol. Fifth, we explored whether baseline hypertension status was an effect modifier for blood pressure and whether baseline glycemic status (HbA1c < or \geq 5.7%) was an effect modifier for glucoregulatory outcomes. We also excluded participants who self-reported having type 2 diabetes at baseline and repeated the LMM analysis. Last, we examined whether changes in MVPA altered the intervention effect estimates by including MVPA at baseline and 3 months as a time-varying covariate, and the MVPA*group interaction in the LMMs.

Gaussian link functions were used in the mixed models, and diagnostic plots were generated to evaluate model assumptions. Insulin, glucose, and HOMA2-IR were log-transformed to better approximate Gaussian distributions, and results were presented as geometric means with 95% CIs derived from model estimates (β coefficients) at baseline and at 3 months, along with mean (95% CI) within group changes. For the other outcomes, sedentary behavior measures, and blood pressure, mean (95% CI) at baseline and 3 months, as well as mean (95% CI) within-group change derived from model parameters (β coefficients), are presented. Treatment effects were calculated as the mean (95% CI) of the difference (compared with the control group) in absolute changes (for all outcomes) and percent changes (for log-transformed outcomes) from baseline to 3 months.

Analyses were implemented in the R statistical programming language, and LMMs were executed by R package nlme. All hypothesis tests were 2-sided. We used significance level $\alpha=0.025$ for the primary analyses to adjust for multiple comparisons (2 intervention groups versus control). No multiple comparison adjustment was made for secondary analyses.

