## Participants

### Eligibility

To be eligible, participants must be female and meet the following inclusion criteria: (1) currently 55 years or older; (2) sit for more than 7 hours on a majority of device-measured days, as assessed by activPAL (as given in the *Screening Visit* section); (3) do 70 or fewer sit-to-stand transitions on a majority of device-measured days, as assessed by activPAL; (4) no health conditions that would inhibit standing; (5) able to read and write fluently in English; (6) postmenopausal, defined as no menstrual period in the last 12 months; (7) BMI $\geq$ 25 kg/m^2 and <45 kg/m^2; (8) able to walk, stand, and perform sit-to-stand transitions without a high risk of falling, determined by the Short Physical Performance Battery (SPPB); and (9) able to travel to study visits. Exclusion criteria include (1) the use of insulin, (2) uncontrolled diabetes defined as HbA1c>10%, (3) uncontrolled blood pressure defined as systolic blood pressure>180 or diastolic blood pressure>110, and (4) participation in another research study or program that would impact the outcomes of this study.

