## **Screening Visit**

At the initial visit, study requirements are reviewed and signed informed consent is obtained. Next, participants complete a medical history questionnaire and self-report their current medication and supplement use to confirm they do not have a medical condition that would inhibit standing or sit-to-stand transitions and do not use insulin. Measurements of height, weight, and blood pressure are taken to screen for BMI and blood pressure. Hip and waist circumference measurements are also recorded. Participants perform SPPB to assess physical functioning and the ability to safely stand and perform sit-to-stand transitions. If all the preliminary screening criteria are met, participants complete a battery of cognitive tests and questionnaires on self-reported demographics and PA. Participants are given an activPAL, a thigh-worn accelerometer that objectively measures sitting time and number of sit-to-stand transitions, and an ActiGraph GT3X+ (ActiGraph, LLC) accelerometer, a waist-worn device that objectively measures minutes of PA. Participants are shown how to attach activPAL using waterproof Tegaderm dressing so that it does not have to be removed, and replacement waterproof dressing is provided. Participants are asked to wear these devices for 24 hours continuously, except they are asked to remove the ActiGraph GT3X+ accelerometer before bathing or swimming for the next 7 days.

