## **Baseline Visit**

Participants return to the clinic after at least seven days of wearing the two devices. Data from activPAL are screened for sitting time (more than 7 hours on a majority of measured days) and sit-to-stand transitions (70 or fewer transitions per day on a majority of measured days) to confirm eligibility. Participants provide fasting blood samples via a finger prick to screen for HbA1c. Those who pass these final eligibility criteria then have a venous blood draw taken by a certified phlebotomist and complete additional questionnaires. Participants receive a total of US \$35 for completing baseline measures. After all baseline assessments are complete, the participants are then randomized.

Randomization is stratified by BMI (overweight vs obese) and employment status (full-time vs nonfull-time employment). A computerized randomization scheme was created using the STAR program grant Biostatistics Core, using a random number generator. A stratified permuted block design is used in this study. After randomization, the participants review the expectations and requirements of their study group assignment (details given in the *3-Month Intervention* section). Data collectors and the principal investigator are blinded to the study group assignment.

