## **3-Month Final Visit**

Before their final visit, participants are mailed the accelerometer and activPAL and asked to wear both devices continuously for 7 days before the visit. At this visit, participants repeat the same measures collected at the screening and baseline visits, including blood draw, anthropometric measures, battery of cognitive tests, SPPB, and questionnaires. Participants receive up to US \$110 for completing the final measures.

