During the first 60-minute in-person session, the health coach provides an overview of the intervention and gives participants a binder of printed educational materials and safety tips, printed action plan forms, and tracking logs. First, participants are asked to share their motivation to join the study. Next, they review reasons for sitting, dangers of prolonged sitting, and benefits of breaking up sitting. Tips for safely reducing sitting or increasing sit-to-stand transitions based on group assignments are reviewed. The health coach models the target behavior by having participants in the Reduce Sitting arm practice standing for up to 5 minutes in the middle of the session, and participants in the Increase Transitions arm perform 3 brief sit-to-stand transitions in a row, holding each for 5 seconds, twice during the session. Participants are then given a wrist-worn activity band that is programmed to prompt sitting breaks based on group assignment (refer to the *Toolbox* section). Participants are shown graphs from activPAL data, either of time spent sitting or sit-to-stand transitions, depending on the group assignment (Figures 1 and 2). The health coach and participants use the graphs to (1) review a typical day and identify times during the day when participants may be able to take sitting breaks or perform sit-to-stand transitions, (2) set behavior change goals for the next week, and (3) create a specific action plan. Participants complete an action plan by identifying the specific strategy, location, days of the week, time of day, and tailored goals for the participant (number of minutes to reduce sitting by or number of transitions to complete). Participants brainstorm potential obstacles to following the action plan and solutions for overcoming each obstacle. Using motivational interviewing techniques, confidence is assessed and supported using a 0 (very low confidence) to 10 (very high confidence) scale (*ruler*). To further support behavior change, participants are provided with several tools they can choose to use. As people vary in their preferences and needs, a toolbox approach allows participants to select tools they want to try (refer to the *Toolbox* section). At the end of the session, participants are given an activPAL to wear for the next 7 days and bring in the following week so that they can review their behavior with their health coach. If the participant provides consent, the health coach sessions are audio recorded for quality checks and training.

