
At each subsequent coaching session, the health coach starts by assessing the adverse events that may have occurred since the last session. Then the health coach and the participant model the respective behavior, gradually increasing the number of minutes of standing or number of transitions each week until week 4, when standing time may be up to 10 minutes and the number of transitions at the beginning of the session may be 5. The health coach reviews any key topics from the previous session before introducing the new behavior change topic (Figure S1 in Multimedia Appendix 1). When worn, the previous week's daily activPAL data are reviewed using daily graphs of data (Figures 1 and 2), as described above for week 1. Graphs of weekly data are shown to discuss progress toward the target behavior (Figures 3 and 4). At each session, the health coach supports the updating of personalized goals and action plans. There is a second break to model the target behavior before completing the action plan. Discussions on barriers and solutions and the confidence to meet the goal are addressed. Weeks 2, 3, 4, and 8 sessions are carried out in person and last approximately 60 minutes each. Weeks 6 and 11 sessions are carried out over the phone and last approximately 30 minutes each. Participants are given activPAL to wear in weeks 1, 2, 3, 4, 8, and 9.

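### The SAP tabulates only study-related adverse events by group; an all-event table by arm, with study-related events as a subset, would remove the dependence on a relatedness judgement that may vary by arm

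*SAP*

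**What the plan says.** The Statistical Plan in the SAP has one sentence on safety: "Study-related adverse events were tabulated by group using a standard medical dictionary for regulatory activities body system categories". It restricts the by-group table to study-related events. Neither document plans a table of all events, defines study-related, or names the person who decided it.

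The protocol adds the following:

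- **Blinding (Baseline Visit):** "Data collectors and the principal investigator are blinded to the study group assignment". Health coaches are not named, and the sentence does not mention adverse events.
- **Enquiry in the two intervention arms (Health Coaching Sessions):** at each session after the first, "the health coach starts by assessing the adverse events that may have occurred since the last session". The enquiry is not limited to related events.
- **Content of the intervention arms (same section):** "The health coach models the target behavior by having participants in the Reduce Sitting arm practice standing for up to 5 minutes". The Increase Transitions arm practises repeated sit-to-stand transitions.
- **Control sessions (Healthy Living):** "At each session, the health coach first provides an introduction to the selected topic". Adverse-event enquiry is not mentioned.
- **Fall risk (Eligibility):** women must be "able to walk, stand, and perform sit-to-stand transitions without a high risk of falling". No falls outcome is described.
- **Oversight (Study Objectives):** an external board reviews participant safety twice a year.

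**The concern.** Randomisation protects a comparison of all events between arms, because no causal judgement is needed to make it. Keeping only the events that someone judged related puts a post-randomisation filter in front of that comparison. The filter may not act equally. A fall is easier to connect with standing or sit-to-stand practice than with a conversation about sleep or safe driving. If so, a difference between arms in the table mixes any real difference in risk with a difference in readiness to attribute.

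Even if attribution were perfectly even, a related-only table leaves out the background events. A reader who sees a few related falls in an intervention arm cannot tell how many falls of any cause occurred in each arm.

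What is at stake is narrow. Pain and physical function have their own measures (SF-36, SPPB and the PROMIS pain forms), so the gap concerns discrete events such as falls. No safety test is planned, and the glucoregulatory and blood pressure analyses are untouched.

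**Working it through.** The plan gives no adverse-event figure to reproduce. The check is first a comparison of texts and then an illustration of how the two kinds of table behave.

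**Texts side by side**

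1. *Scope of the table.* The SAP sentence sets a rule (related events only), and nothing elsewhere widens it.
2. *Who asks.* In the intervention arms the coach asks. The coach delivers the arm content and so knows the arm.
3. *Who judges relatedness.* Not stated. The coach's enquiry is not described as a causality judgement, and the blinding of the principal investigator and data collectors is not described as covering one.
4. *Whether all arms were asked.* Enquiry is written down for intervention follow-up sessions only. At the final visit, "participants repeat the same measures collected at the screening and baseline visits, including blood draw, anthropometric measures, battery of cognitive tests, SPPB, and questionnaires". That list is not presented as complete, and at the screening visit "participants complete a medical history questionnaire and self-report their current medication and supplement use", so some health enquiry common to all arms is possible.

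**Illustration (every rate below is assumed)**

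Inputs: 405 women planned (Study Objectives); equal allocation assumed, so 405/3 = 135 per arm; the same true risk in every arm, 10% (range 5% to 20%). For simplicity each affected participant has one event, and capture does not depend on relatedness.

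- All-events count = n × risk × capture
- Related-only count = n × risk × capture × share judged related
- Participants with an event: 135 × 0.10 = 13.5 per arm (135 × 0.05 = 6.75; 135 × 0.20 = 27)

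| Capture, intervention / control | Judged related, intervention / control | Related-only table | Ratio | All-events table | Ratio |
|---|---|---|---|---|---|
| 100% / 100% | 40% / 40% | 5.4 vs 5.4 | 1 | 13.5 vs 13.5 | 1 |
| 100% / 100% | 40% / 20% | 5.4 vs 2.7 | 2 | 13.5 vs 13.5 | 1 |
| 100% / 100% | 40% / 10% | 5.4 vs 1.35 | 4 | 13.5 vs 13.5 | 1 |
| 100% / 100% | 20% / 40% | 2.7 vs 5.4 | 0.5 | 13.5 vs 13.5 | 1 |
| 100% / 50% | 40% / 40% | 5.4 vs 2.7 | 2 | 13.5 vs 6.75 | 2 |
| 100% / 50% | 40% / 20% | 5.4 vs 1.35 | 4 | 13.5 vs 6.75 | 2 |

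At 5% or 20% risk the counts halve or double and the ratios stay the same.

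With equal true risk, the related-only ratio is (capture ratio) × (attribution ratio), and the all-events ratio is the capture ratio alone. The all-event table removes the attribution factor. It does not remove the capture factor. The ratios restate the assumed shares and are not evidence of what happened in this trial.

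**Could the all-event table support a test?** With 135 per arm, two-sided 0.05 and the usual normal approximation, power is 0.344 for 5% vs 10% and 0.635 for 10% vs 20%. It should be read as descriptive.

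**The case against.** The strongest reply is that bias is not shown. Relatedness is undefined, so nothing in the documents establishes that it depends on arm content; some related events, such as those from blood draws, come from procedures common to all arms. A blinded investigator may have made every judgement. The protocol text calls itself a paper, so its silence on adverse-event procedure says little about practice. The external board reviewed safety, women at high risk of falling were excluded, and the table is descriptive. All of this stands, and it limits the point to what may happen. It does not supply a background rate by arm, which is missing even under blinded and even-handed attribution. Board review is also not described as a by-arm comparison of all events.

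A second reply is that the remedy has the same weakness as the table it replaces. The one asymmetry visible in the text is in enquiry, and unequal enquiry would distort an all-event table too. This also stands, as the unequal-capture rows show, and it is why the elicitation note has to accompany the table.

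Two stronger readings are tempting. A reader might infer that the unblinded coach decided relatedness. The protocol says only that the coach asked about events. A reader might also infer that control participants were not asked about adverse events. The Healthy Living section does not mention it, but that is silence, and the final visit may have included a health enquiry in all arms.

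**Conclusion.** The point holds as a low-cost improvement to safety reporting. The SAP's rule filters the by-group table on a judgement that may depend on arm and whose maker and blinding are not stated. The table may therefore carry attribution bias, and it omits the background events needed to read discrete events such as falls. The size is unknown, and so is the direction: attribution could be even, could favour either arm, or could be offset or compounded by unequal enquiry. The documents do not support saying that the table is biased. The conclusion rests on two inferences: that an event is more readily linked to physical practice than to health-topic discussion, and that the SAP sentence is the full safety analysis. No efficacy estimate, planned test or significance level changes.

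**What to change.** In the SAP, replace the related-only rule with a table of all recorded adverse events by arm, regardless of relatedness. Show participants with at least one event and the number of events by body system, with study-related events as a subset.

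Beside the table, state how events were elicited in each of the three arms, how study-related was defined, who judged it and whether that person knew the arm. If elicitation differed between arms, say that between-arm differences are not to be interpreted as treatment harm.

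The cost is one extra descriptive table and a short note, with no new data collection if the events are on record. The coach's enquiry was not limited to related events and an external board reviewed safety, so fuller listings may exist, but the documents do not say so. If unrelated events were not recorded, state that as a limitation of the related-only table.
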